7.4.2 Analysis of Secondary Efficacy Endpoints

The secondary endpoints defined below are binary with yes/no outcomes. These secondary endpoints will be analyzed on FAS using the same method for the primary efficacy endpoint analysis described in Section [7.4.1.1](#)

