7.4.2 Analysis of Secondary Efficacy Endpoints

The secondary efficacy endpoints in this study include:

- Incidence of adjudicated CMV disease, including CMV syndrome and CMV tissue-invasive disease through one year post first Study Drug injection.
- Incidence of CMV viremia (defined as plasma viral load \geq the lower limit of quantification [LLOQ]) by central assay through one year post first Study Drug injection.
- Incidence of adjudicated CMV-specific antiviral therapy.
- Incidence of graft survival through one year post Study Drug injection.
- Incidence of subject survival through one year post Study Drug injection.

The secondary efficacy endpoints will be each analyzed using the same CMH method described in 7.4.1.1.

All analyses of secondary endpoints will be performed using FAS and PPS.

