6.1.2 Secondary Efficacy Endpoints

Secondary efficacy endpoints are: :

- Proportion of subjects with Adjudicated CMV-associated disease including CMV syndrome and CMV tissue-invasive disease.
- Proportion of subjects with plasma viral load \geq the lower limit of quantification [LLOQ] assessed by central laboratory.
- Proportion of subjects who took Adjudicated CMV-specific antiviral therapy for the treatment of CMV viremia or disease.
- Proportion of subjects with graft survival.

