7 STATISTICAL METHODOLOGY

7.1 General Considerations

All statistical analyses and summary information will be generated according to this analysis plan and any deviations from this plan will be documented in the clinical study report. Any numerical rounding should be performed at the end of calculations. The p-values will be displayed with 3 decimal places. Statistical significance will be determined prior to rounding the p-value.

For continuous variables, descriptive statistics will include the number of subjects (n), mean, standard deviation, median, minimum and maximum. Frequencies and percentages will be displayed for categorical data. Percentages by categories will be based on the number of subjects with no missing data thus the percentages will add up to 100%. Baseline will be the last non-missing value on or prior to first study drug unless otherwise specified.

All efficacy comparisons will be tested at the 1-sided 0.05 significance level. Confidence intervals for efficacy estimates, if provided, will be constructed at 2-sided 90% level.

All data processing, summarization, and analyses will be performed using SAS® Version 9.1.3 or higher on Unix.

This SAP includes the data analysis for the primary study period (ie, 1-year post first study drug injection) which is defined as data collected through day 380 (=365+14+1 day). Certain data summary will consider analysis window as specified in each section. The long-term follow-up period is not covered by this SAP and will be managed in a separate SAP.

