7.4 Analysis of Efficacy

7.4.1 Analysis of Primary Endpoint

7.4.1.1 Primary Analysis of Primary Efficacy Endpoint

The primary efficacy endpoint is the proportion of subjects with CMV viremia which is defined as plasma viral load ≥ 1000 IU/mL assessed by central assay through one year post first Study Drug injection. CMV viral load tests are scheduled once every 2 weeks for the first 8 tests starting 100 days from transplant and subsequently once per month for 7 more tests. In addition, a subject may have unscheduled tests (suspect CMV syndrome or CMV tissue-invasive disease) by the local laboratory so that the subject can be treated promptly with antiviral therapy (AVT) if needed. Everytime a local laboratory is performed, the sample should also be sent to the central laboratory for assessment. The CMV viral load collected from the central laboratory after first injection (Day 1) through day 380 ($=365+14+1$) that were collected as scheduled or unscheduled assessments will be utilized.

A patient who discontinue the study without a positive CMV viral load will be imputed as having a CMV viremia. A patient who has more than one time with viral load ≥ 1000 IU/mL by central assay will be counted once in this summary. Any unscheduled central laboratory values within the window will be included.

A Cochran-Mantel-Haenszel (CMH) test at the 1-sided 5% level stratified by use of anti-thymocyte globulin (ATG) and by receipt of a kidney from a living or deceased donor will be used to analyze the primary endpoint of CMV incidence rate.

The null and alternative hypotheses for this comparison are:

H0: Common Odds Ratio = 1.

H1: Common Odds Ratio < 1.

The odds ratio is defined as the ratio of odds of viremia in the ASP0113 group to that in the placebo group. The 1-sided p-value with the 2-sided exact 90% confidence interval for the

common odds ratio will be calculated (in SAS specifying the comor option in the exact statement of proc freq).

The primary analysis will be conducted for the FAS population.

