7.4.2.3 Graft Survival

Calculation of graft survival: any subject that does not fit the definition of graft loss as follows during the primary study period will be defined as “yes”: subject death, re-transplant, nephrectomy, or return to permanent dialysis (i.e., for >30 days). The proportion of subjects with graft survival will be analyzed.

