9.4 Appendix 4: List of the SAP Changes and Rationale

The changes to the approved SAP (15April 2014) that affect the analyses are specified with the rationale in the table below.

SAP Sections	Description	Rationale
5.2 Per Protocol Set (PPS)	Removed.	For a Phase 2 study, this type of analysis where a sizable number of patients are excluded from the PPS classification criteria may provide uninterpretable results.
6.1.2 Secondary Efficacy Endpoints	Removed one of the secondary efficacy endpoint of subject survival through one year.	In order to avoid redundancy as as the mortality is summarized as a part of adverse event summary.
7.1 General Consideration	Specified the analysis duration of the primary study period as data collected through day 380 (=365+14+1) for this SAP.	This analysis duration is specified by taking the protocol allowed visit windows in order to clarify the data inclusion for this analysis plan.
7.2.2 Protocol Deviation	Removed the category of PD5-Other.	In order to capture the protocol deviations to specific categories utilizing PD1 through PD4.
7.4.1.2 Sensitivity Analysis for Primary Efficacy Endpoint	
 Clarified the analysis to assume a patient with at least 2 consecutive missing central laboratory viral load as a CMV viremic, and Added an analysis to consider a patient who took AVT that is adjudicated as a CMV viremia treatment but no evidence of CMV viremia by central laboratory is assumed CMV viremic. 	These sensitivity analyses are planned in order to evaluate the robustness of the primary analysis for the primary efficacy endpoint.
7.4.3 Analysis of Exploratory Endpoints	The assessments of kidney transplantation and SF-12 questionnaires to be only listed without a formal analysis within this analysis plan.	A proper analysis for these questionnaires to be conducted by the HEOR expert.
7.5.2 Adverse Events of Special Interest	Removed the following AEs of special interest: 
 Opportunistic infections Special infections related to kidney transplant Post-transplant lymphoproliferative disorder 	The opportunistic infection is a prespecified exploratory efficacy endpoint thus removed from this section in order to avoid redundancy. The second and third bullet items are removed because these events are not expected to occur under vaccine treatment.

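### The one-sided test carried over to graft survival points the wrong way: its only stated alternative is an odds ratio below 1, but benefit on this endpoint is an odds ratio above 1

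*SAP*

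**What the plan says.** SAP 7.4.1.1 sets the primary test: Cochran-Mantel-Haenszel, one-sided 5%, stratified by anti-thymocyte globulin use and donor type, with a two-sided exact 90% confidence interval for the common odds ratio. The alternative is "H1: Common Odds Ratio < 1", and the orientation is explicit: "The odds ratio is defined as the ratio of odds of viremia in the ASP0113 group to that in the placebo group".

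SAP 7.1 applies the sidedness to everything: "All efficacy comparisons will be tested at the 1-sided 0.05 significance level". It gives no direction by endpoint.

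SAP 7.4.2 then carries the primary method over: "These secondary endpoints will be analyzed on FAS using the same method for the primary efficacy endpoint analysis". Four endpoints fall under that sentence: adjudicated CMV disease, viral load at or above the LLOQ, adjudicated CMV-specific antiviral therapy, and graft survival. SAP 6.1.2 lists the last as "Proportion of subjects with graft survival". SAP 7.4.2.3 fixes its coding: "any subject that does not fit the definition of graft loss as follows during the primary study period will be defined as" a yes. Graft loss there means death, re-transplant, nephrectomy or permanent dialysis.

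The protocol has the same carry-over in its section 7.4.2: "The secondary efficacy endpoints will be each analyzed using the same CMH method described in 7.4.1.1". Its own 7.4.1.1 has the same alternative but does not say which arm is the numerator. Its list also includes subject survival, which the SAP has since dropped (Appendix 4: "Removed one of the secondary efficacy endpoint of subject survival through one year").

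**The concern.** An odds ratio below 1 means benefit only when the counted outcome is unfavourable. That holds for viremia and for the first three secondary endpoints. For graft survival the counted outcome is the favourable one, so the carried-over alternative is that the vaccine lowers graft survival.

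A one-sided test is defined by the direction stated in advance. Here the only stated direction is the harm direction. A programmer who reuses the primary code with yes as the event reports the harm tail. One who reverses the tail departs from the written method, and SAP 7.1 requires departures to be documented in the study report. Because the endpoint counts deaths and graft losses, a small p-value produced by harm and listed among the efficacy results would be misleading.

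**Working it through.** **Direction, endpoint by endpoint** (odds ratio = vaccine over placebo)

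| Secondary endpoint (SAP 6.1.2) | Outcome counted | Benefit means | Carried-over alternative |
|---|---|---|---|
| Adjudicated CMV disease | unfavourable | OR < 1 | fits |
| Viral load at or above LLOQ | unfavourable | OR < 1 | fits |
| CMV-specific antiviral therapy | unfavourable | OR < 1 | fits |
| Graft survival | favourable | OR > 1 | wrong tail |

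SAP 7.4.2.2 adds an endpoint-specific rule (imputation for the LLOQ endpoint). SAP 7.4.2.3 adds nothing on direction.

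**The plan's own figure.** No figure is stated for graft survival. The sample size does confirm that the primary method is one-sided 5%. With 46% versus 25%, the mean rate is 0.355:

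n = [1.645·√(2·0.355·0.645) + 0.842·√(0.46·0.54 + 0.25·0.75)]² / 0.21² = (1.113 + 0.556)² / 0.0441 ≈ 63.2, so 64 per arm, as stated (power 80.5%). A two-sided test would need 81.

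**Size of the effect.** All graft-loss counts below are assumptions, with 70 per arm and one stratum. With *a* survivors on vaccine, *m* survivors in total and N = 140:

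- E = 70·m/140
- V = 70·70·m·(140 − m) / (140²·139)
- Z = (a − E)/√V
- p as written = Φ(Z); p in the benefit direction = 1 − Φ(Z)

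Example, losses 8 placebo and 1 vaccine: a = 69, m = 131, E = 65.5, V = 2.1205, Z = 3.5/1.4562 = 2.40. As written p = 0.992; in the benefit direction p = 0.008. Exact p-values are hypergeometric tails.

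| Losses, placebo / vaccine | p as written (exact) | p in benefit direction (exact) |
|---|---|---|
| 5 / 1 | 0.952 (0.986) | 0.048 (0.104) |
| 8 / 3 | 0.941 (0.972) | 0.059 (0.104) |
| 8 / 1 | 0.992 (0.9985) | 0.008 (0.017) |
| 1 / 5 (harm) | 0.048 (0.104) | 0.952 (0.986) |
| 1 / 8 (harm) | 0.008 (0.017) | 0.992 (0.9985) |

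Recoding to graft loss with OR < 1 gives the same values as the right-hand column. With 64 per arm every p-value moves by no more than 0.001. Spreading 8 versus 1 losses over four strata gives 0.991 as written and 0.009 in the benefit direction.

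**Rejection rates** (assumed true rates, 70 per arm, unstratified normal approximation). If survival were 95% on vaccine and 90% on placebo, the test as written rejects 0.4% of the time and the correctly directed test 31%. For 98% versus 90% the figures are 0.02% and 70%. If the vaccine were worse, 90% versus 98%, the test as written would reject 70% of the time.

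**What the confidence interval shows.** In the 1 / 8 harm case the survival odds ratio is 0.11, exact 90% interval 0.005 to 0.71. In the mirror benefit case it is 8.9, interval 1.41 to 197.

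**The case against.** The strongest reply is that the hypotheses in SAP 7.4.1.1 are worded for viremia, so what carries over is the machinery (stratified test, one-sided 5%, exact interval) and not the direction. On that reading the direction for graft survival is unstated, not reversed. Since graft survival is listed as an efficacy endpoint, any statistician would test for higher survival on vaccine. The two asymptotic tails are complements, and the two-sided 90% interval supports one-sided 5% inference either way, so a reader could recover the answer.

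Part of this stands. The wrong tail follows from reading the cross-reference literally, and the interval and proportions would expose a mistake. But the alternative reading leaves a one-sided test with no stated alternative, and the same sentence is needed to repair it. That the intent is obvious does not replace pre-specification.

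Two further points stand. The counts are invented. And SAP 7.4.3 calls the 7.4.1.1 procedure exact, so the exact p-values are the relevant ones. On those, 5 versus 1 and 8 versus 3 miss 0.05 in either direction, and among these examples only the 8 versus 1 split and its mirror change a significance conclusion.

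For the protocol, the orientation of the odds ratio is not given, so its text is ambiguous and cannot be called wrong-tailed.

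**Conclusion.** The concern holds. The SAP's only stated alternative, applied as SAP 7.4.2 directs to graft survival as SAP 7.4.2.3 codes it, tests for harm. No passage in either document corrects this.

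The consequence is confined to the one-sided p-value of one secondary endpoint in a phase 2 trial. The primary test, sample size and futility rule are unaffected, as are the odds-ratio estimate and its interval for graft survival. The reversal of direction follows from the text alone; its numerical size depends on graft-loss counts that the documents do not give. It should be fixed before unblinding, because choosing the tail afterwards is the discretion a SAP exists to remove.

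**What to change.** In SAP 7.4.2.3, do one of two equivalent things:

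- analyse the proportion with graft loss (the existing four-part definition) and keep the alternative of an odds ratio below 1; or
- keep graft survival and state that the alternative is a common odds ratio above 1, vaccine over placebo.

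The first leaves all four secondary endpoints with the same direction and lets the primary code be reused.

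Add a matching sentence to Protocol 7.4.2, with the orientation of the odds ratio stated. Word it to cover subject survival too, since the protocol still lists it. Subject survival needs no change in the SAP.

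The cost is one sentence in each document, with no new data and no change to the primary analysis or sample size.

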7.4.2.1 Adjudicated Endpoints

An independent panel of medical experts will adjudicate the events below through one year post first study drug injection based on blinded data:

- CMV associated disease including CMV syndrome and tissue invasive disease,
- CMV specific antiviral therapy for the treatment of CMV viremia or disease

The proportion of subjects with any of the two adjudicated events will be analyzed separately

7.4.2.2 CMV Viremia Defined as Plasma Viral Load \geq the Lower Limit of Quantification [LLOQ] by Central Assay

The central laboratory will have the LLOQ for CMV viral load assessment. When the viral load is below the LLOQ the actual viral load reading is not possible and will be denoted as \leq LLOQ. If a subject has any CMV viral load assessment greater than the LLOQ by central laboratory the subject will be classified as viremic. The proportion of subjects with viremia will be analysed. For the purpose of this analysis, the same imputation method should be used as for the primary analysis.

7.4.2.3 Graft Survival

Calculation of graft survival: any subject that does not fit the definition of graft loss as follows during the primary study period will be defined as “yes”: subject death, re-transplant, nephrectomy, or return to permanent dialysis (i.e., for >30 days). The proportion of subjects with graft survival will be analyzed.

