In a recent study of prophylactic valganciclovir given at 900 mg/day for 100 days to donor CMV-seropositive/recipient CMV seronegative (D+R-) kidney transplant recipients (Humar, 2006), CMV viremia, defined as CMV viral load > 600 copies/mL, was seen through one year in 83 of 163 subjects [50.9%, 95% CI = (43.0%, 58.8%)]. In another study (Couzi, 2012), CMV infection, defined as two consecutive positive Polymerase Chain Reaction (PCR) assay results, was seen in 11 of 32 subjects [34.4%, 95% Confidence Interval (CI) = (18.6%, 63.2%)], respectively. Pooled from these two studies by weighted average, it is estimated that placebo rate is 46% (70% weight on Humar's result). A sample size of 64 subjects per arm will allow the study to have 80% power to detect a reduction in CMV viremia to 25% due to ASP0113 at 52 weeks using a 1-sided test with a type 1 error rate of 5%. To allow for loss to follow-up, 70 subjects per arm will be enrolled for a total sample size of 140 subjects.

Efficacy:

The Full Analysis Set (FAS) to be used for primary analysis of the primary efficacy variable will consist of all randomized subjects who receive at least one Study Drug injection and have at least one post dose viral load assessment by central laboratory. The FAS will be used for all efficacy analyses.

The primary analysis of the incidence of CMV viremia will consist of a Cochran-Mantel-Haenszel (CMH) test stratified by the factors used in the stratified randomization. Subjects who are lost to follow-up will be assumed to have met the primary endpoint. The secondary variables will each be similarly analyzed.

The event rates of the secondary variables will each be compared between treatments using the same CMH method as in the primary analysis. The survival endpoints (time to first event) will be analyzed using a Cox proportional hazards model. The Cox model will include the randomization factors. The common hazard ratio and confidence limits will be estimated. The 1-sided p-values for testing the hypothesis that the hazard ratio is equal to unity will be calculated. The Kaplan-Meier survival curves for the treatment groups will be displayed.

Pharmacogenomics:

Subjects who consent to participate in the optional pharmacogenomics sub-study will have a whole blood sample collected during the Baseline visit, after Randomization but prior to the first Study Drug injection, for exploratory retrospective pharmacogenomics (PGx) analysis.

Safety:

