5.3.2 Secondary Efficacy Assessments

- Adjudicated CMV disease: CMV syndrome and CMV Tissue Invasive Disease as defined in Appendix 7
- CMV Plasma Viral Load by Central Assay
- Adjudicated CMV-specific AVT for CMV viremia or CMV disease

Initiation of AVT with activity against CMV will be adjudicated by an Adjudication Committee as set forth in the Adjudication Charter.

- Graft Survival

Graft survival is defined as any subject that does not fit the definition of graft loss as follows: graft loss is defined as subject death; re-transplant; nephrectomy; or return to permanent dialysis (i.e., for > 30 days) at Study Month 13./Day 395 and 6 months after Day 395 then, annually for the next 4 years.

- Subject Survival

Subject survival is any subject that is known to be alive at Study Month 13/Day 395. For the Long Term Follow Up period, patient survival is any subject that is known to be alive at the conclusion of the Long Term Follow-Up period.

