4 SAMPLE SIZE

In a recent study of prophylactic valganciclovir given at 900 mg/day for 100 days to donor CMV-seropositive/recipient CMV seronegative (D+R-) kidney transplant recipients [Humar, 2006], CMV viremia, defined as CMV viral load \geq 1000 IU/mL, was seen through one year in 83 of 163 subjects [50.9%, 95% CI = (43.0%, 58.8%)]. In another study [Couzi, 2012], CMV infection, defined as two consecutive positive Polymerase Chain Reaction (PCR) assay results, was seen in 11 of 32 subjects (34.4%, 95% Confidence Interval (CI) = (18.6%, 63.2%)), respectively. Pooled from these two studies by weighted average, it is estimated that placebo rate is 46% (70% weight on Humar's result). A sample size of 64 subjects per arm will allow the study to have 80% power to detect a reduction in CMV viremia to 25% due to ASP0113 at 52 weeks using a 1-sided Chi-square test with a type 1 error rate of 5%. To allow for drop-out (randomized but not evaluable), 70 subjects per arm will be enrolled for a total sample size of 140 subjects.

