7.9 Handling of Missing Data, Outliers, Visit Windows, and Other Information

7.9.1 Missing Data

In the analysis of the primary endpoint, subjects who are lost to follow-up will be imputed as having viremia. Otherwise, viremia will not be imputed. Only observed viral loads from central labs meeting the definition of viremia will be counted.

Time to event variables will be considered censored at the time of the last assessment. Time to the first protocol-defined CMV viremia will be considered censored at the time of the last recorded central laboratory CMV measurement.

The start and stop dates of AEs and concomitant medication will be imputed to allocate the concomitant medication and AEs to a treatment group, in addition to determining whether an AE is/is not treatment emergent. Listings of the AEs and concomitant medications will present the actual partial dates; imputed dates will not be shown.

In case of missing partial start and stop dates for concomitant medications, the following rules will be used:

If start date is missing or partial:

- if month is missing, use January
- if day is missing, use the first day of the month under consideration
- if year is missing, use year of the informed consent date
- if entire date is missing, use informed consent date

If stop date is missing or partial:

- if month is missing, use December
- if day is missing, use the last day of the month under consideration
- if year or the entire date is missing, set to December 31st, 2099

If the imputed start date is after the stop date, then the imputed start date will be one day prior to the stop date.

For AEs, a missing or incomplete onset date will be imputed according to the following conventions for the purpose of defining TEAE.

- 1) Missing year, the AE will be count as TEAE
- 2) Missing month, the AE will be counted as TEAE if the year is equal to the consent year or one year later.
- 3) Missing date, using the last date of the month to determine TEAE.

No imputation of missing data for other variables will be done.

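### Early leavers with unknown graft status are scored as graft survivors, and the SAP gives three conflicting scorings of early leavers for adjudicated CMV disease and antiviral therapy

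*SAP*

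**What the plan says.** **Primary endpoint.** SAP 7.4.1.1 imputes viremia for a subject who discontinues the study without a positive viral load. SAP 7.9.1 states the rule for subjects lost to follow-up.

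**Graft survival.** SAP 7.4.2.3: "any subject that does not fit the definition of graft loss as follows during the primary study period will be defined as" a yes. Graft loss means death, re-transplant, nephrectomy or permanent dialysis. Nothing requires that the subject was followed or that the graft was known to function. Protocol 5.3.2 uses the same default, yet defines the neighbouring endpoint the other way: "Subject survival is any subject that is known to be alive at Study Month 13/Day 395".

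**Viremia at or above the LLOQ.** SAP 7.4.2.2 carries the primary rule over explicitly: "the same imputation method should be used as for the primary analysis".

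**Adjudicated CMV disease and AVT.** SAP 7.4.2.1 gives no rule for early leavers. Three other places bear on it:
- SAP 7.4.2 refers the secondary endpoints to the primary-endpoint method in 7.4.1.1.
- SAP 7.9.1 ends: "No imputation of missing data for other variables will be done".
- SAP 7.1 bases percentages on subjects without missing data.

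**Protocol.** The synopsis says: "Subjects who are lost to follow-up will be assumed to have met the primary endpoint. The secondary variables will each be similarly analyzed". Its next paragraph, and Protocol 7.4.2, mention only the shared CMH test. Protocol 7.9 states the imputation for the primary efficacy analysis.

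**Survival.** SAP Appendix 4 records: "Removed one of the secondary efficacy endpoint of subject survival through one year". The reason given is that mortality appears in the adverse event summary.

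**The concern.** One early leaver can be a failure on viremia and a success on graft survival, with no reason given. For CMV disease and AVT the programmer has to choose among three codings. If that choice is made after unblinding, it is open to challenge. If drop-out differs by arm, the choice can change the sign of the between-arm difference.

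The planned sensitivity analyses (SAP 7.4.1.2) address the primary endpoint only. Time to first adjudicated CMV disease has a censored analysis (SAP 7.4.3). Graft loss and AVT have none.

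Deaths are a related gap. After consent is withdrawn, Protocol 6.1.1 follows the subject only for mortality through public records. The SAP does not say whether such deaths enter the death count or the graft-loss derivation, although death is part of the definition of graft loss.

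**Working it through.** **The plan's own figure.** SAP section 4 says "it is estimated that placebo rate is 46" percent and sizes the trial "to detect a reduction in CMV viremia to 25% due to ASP0113 at 52 weeks", with a one-sided 5% test and 80% power. With pooled variance and no continuity correction:

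n = [1.645·√(2·0.355·0.645) + 0.842·√(0.46·0.54 + 0.25·0.75)]² / 0.21² = 63.1, so 64 per arm (power 80.5%).

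This reproduces the SAP and is unaffected by the present point. Enrolling 70 leaves 70 − 64 = 6 per arm, or 6/70 = 8.6%.

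**Assumptions.** Six leavers per arm have no recorded event and are all in the FAS. The documents give no graft-loss or CMV-disease rates, so the rate r among the 64 followed subjects is assumed.

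**Graft survival, 6 of 70 leaving per arm**

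| Assumed loss r | Leavers as survivors: 1 − 64r/70 | Leavers excluded: 1 − r | Leavers as losses: 64(1 − r)/70 |
|---|---|---|---|
| 2% | 98.2% | 98.0% | 89.6% |
| 5% | 95.4% | 95.0% | 86.9% |
| 10% | 90.9% | 90.0% | 82.3% |

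The first column exceeds the second by 6r/70, which is 0.2, 0.4 and 0.9 points. The first exceeds the third by 6/70 = 8.6 points whatever r is. For 3 or 10 leavers that range is 4.3 or 14.3 points.

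**CMV disease, 6 of 70 leaving per arm**

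| Assumed rate r | Leavers as non-events: 64r/70 | Leavers excluded: r | Leavers as events: (64r + 6)/70 |
|---|---|---|---|
| 5% | 4.6% | 5.0% | 13.1% |
| 10% | 9.1% | 10.0% | 17.7% |
| 20% | 18.3% | 20.0% | 26.9% |

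**Unequal drop-out.** Suppose 8 leave on ASP0113 and 4 on placebo, with the same disease rate r among followed subjects in both arms. The difference, ASP0113 minus placebo, should be zero.
- Non-event coding: (62r − 66r)/70 = −0.6 points at r = 10% and −1.1 at r = 20%, favouring ASP0113.
- Event coding: (62r + 8 − 66r − 4)/70 = +5.1 points at r = 10% and +4.6 at r = 20%, favouring placebo.
- Exclusion: 0.

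**A sharper imbalance.** Suppose 9 leave in one arm and 3 in the other, with 10 observed cases in each.
- Non-event coding: 10/70 against 10/70, a difference of 0.
- Exclusion: 10/61 = 16.4% against 10/67 = 14.9%, 1.5 points.
- Event coding: 19/70 = 27.1% against 13/70 = 18.6%, 8.6 points.

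**The case against.** A reader might infer that the SAP declares early leavers free of CMV disease and AVT. It does not. The no-imputation line in 7.9.1 points that way, and the explicit carry-over in 7.4.2.2 suggests that imputation is not automatic elsewhere. But 7.4.2 refers to the section that contains the failure imputation, and 7.1 permits exclusion. The rule is unsettled.

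A reader might also infer that the SAP breaks a protocol rule. The graft default comes from Protocol 5.3.2. The synopsis sentence can be read as sharing only the CMH test, as Protocol 7.4.2 and 7.9 suggest.

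Nor is 8.6 points the bias. It is the gap between two extreme codings. With 3 losses, for example, graft survival is 67/70 = 95.7% as written and 61/64 = 95.3% among followed subjects. The six leavers may also be too many for the FAS. SAP section 4 describes the allowance as subjects who are not evaluable, and SAP 5.1 excludes anyone without a post-dose central viral load.

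Mandatory failure imputation is tempting for consistency with the primary endpoint, but the documents do not clearly require it. In both unequal drop-out examples it produces the largest artificial difference.

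There are mitigations. Subjects who only stop treatment, including for graft failure, stay in follow-up (Protocol 6.1.1). Those who withdraw should have a completion visit within 14 days (Table 1, footnote 23). CMV-disease episodes are modelled with a follow-up offset (SAP 7.4.3), and AVT enters a composite sensitivity analysis of the primary endpoint (SAP 7.4.1.2). Removal of subject survival is logged with a reason, and deaths are tabulated (SAP 7.5.1).

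These arguments limit the size of the problem. They do not supply a requirement for known graft status or a scoring rule for CMV disease and AVT.

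**Conclusion.** The point stands in two parts. Graft survival treats unknown status as success, the opposite of the primary endpoint's treatment of the same subject. For adjudicated CMV disease and AVT, three SAP sections yield three codings and the protocol does not choose among them.

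With balanced drop-out the graft bias is about 0.2 to 0.9 points, given 6 of 70 leavers per arm, assumed loss rates of 2% to 10%, and leavers at the same risk as those followed. It would be larger if leavers lose grafts more often, up to the 8.6-point bound. With unequal drop-out, the sign of a between-arm difference can depend on the coding. The primary test and the sample size are not affected. This is a correction to make before unblinding, not a flaw in the main conclusion of the trial.

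**What to change.** 1. Before unblinding, reconcile SAP 7.4.2, 7.9.1 and 7.1 by stating, for each secondary endpoint, how a subject without follow-up to Day 380 is scored. Use one definition of early leaver, since 7.4.1.1 and 7.9.1 word it differently. LLOQ viremia already has its rule in 7.4.2.2.
2. In SAP 7.4.2.3, do not score unknown graft status as known survival. Report the number with unknown status per arm. Add Kaplan-Meier estimates with a log-rank test, censored at last contact, for graft loss and adjudicated AVT, as SAP 7.4.3 already plans for time to CMV disease.
3. For graft loss, CMV disease and AVT, show leaver-as-failure coding only as a sensitivity bound, not as the main analysis.
4. State that deaths found through public records within the primary study period count in the death total and in the graft-loss derivation.

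The cost is SAP wording and a few table programs, with no new data collection. Stated graft survival would become slightly less favourable.
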